#### SECTION V: POTENTIAL BENEFITS

**Potential Benefits:** Identify any benefits that may be reasonably expected to result from the research, either to the subject(s) or to society at large. (Payment of subjects is not considered a benefit in this context of the risk benefit assessment.)

Individuals who participate in this study will have access to their health data along with the choice and ability to share it with researchers through the Hugo platform. Patients will be contributing to an advancement in the understanding of expected outcomes from novel wearable medical technologies, including the Apple Watch – which is already used by hundreds of thousands of individuals. Participants will also have the option of continuing access to their data at the end of the study, if they so wish, and receive updates to the Hugo Health platform. Using the provided Apple Watch, participants may also gain additional awareness and information regarding their heart rate, rhythm, health, and activity; using the provided Withings Move, participants may gain additional awareness and information regarding their activity.

#### SECTION VI: RESEARCH ALTERNATIVES AND ECONOMIC CONSIDERATIONS

1. **Alternatives:** What other alternatives are available to the study subjects outside of the research?

The alternative to participating in the proposed study is to not participate. Participation and non-participation will have no impact on the course of treatment that the patient will receive.

2. **Payments for Participation (Economic Considerations):** Describe any payments that will be made to subjects, the amount and schedule of payments, and the conditions for receiving this compensation.

Patients who are not randomized to receive the Apple Watch will receive a small stipend for their time contributed as part of this study. An estimated hourly stipend based on the average minimum wage in Connecticut (\$10) will be provided. This will result in a total stipend of up to \$80.

These payments will be made via a Visa pre-paid card through the platform Tremendous which is linked to the Hugo platform. As surveys are completed, the balance will be automatically credited to the patient's account which is linked to the email address they used to set up their Hugo account. Patients will receive payments every 30 days when they respond to the study surveys. When these payments are ready, patients will receive an email with instructions on how to redeem their payment. The Visa card will then be sent to

their email as a digital ecard. Patients may redeem their payments at any time once they have accrued a balance.

Patients in the Apple Watch arm will be given the necessary Apple Watch to keep. The fair market value of this device is \$399.00. Patients in the Withings arm will be provided with a Withings Move to keep. The fair market value of this device is \$69.95.

3. **Costs for Participation (Economic Considerations):** Clearly describe the subject's costs associated with participation in the research, and the interventions or procedures of the study that will be provided at no cost to subjects.

The platform, technology, devices, and apps used in this study will be provided to participants free of cost. Updates to the platform will also be provided free of cost for the duration of the study. Participants will still be responsible for any costs associated with routine follow-ups or doctor's visits, as they would be in the normal processes of care. Participants will still be responsible for any co-pay required by their insurance company for standard treatments. Participants are responsible for data charges that may be incurred for utilizing the online features of Hugo, Withings, or Apple Watch when not connected to Wi-Fi.

4. **In Case of Injury:** This section is required for any research involving more than minimal risk, and for minimal risk research that presents the potential for physical harm (e.g., research involving blood draws).
  - a. Will medical treatment be available if research-related injury occurs? *Write here*
  - b. Where and from whom may treatment be obtained? *Write here*
  - c. Are there any limits to the treatment being provided? *Write here*
  - d. Who will pay for this treatment? *Write here*
  - e. How will the medical treatment be accessed by subjects? *Write here*

#### IMPORTANT REMINDERS

Will this study have a billable service? Yes  No

*A billable service is defined as any service rendered to a study subject that, if he/she was not on a study, would normally generate a bill from either Yale-New Haven Hospital or Yale Medical Group to the patient or the patient's insurer. The service may or may not be performed by the research staff on your study, but may be provided by professionals within either Yale-New Haven Hospital or Yale Medical Group (examples include x-rays, MRIs, CT scans, specimens sent to central labs, or specimens sent to pathology). Notes: 1. There is no distinction made whether the service is paid for by the subject or their insurance (Standard of Care) or by the study's funding mechanism (Research Sponsored). 2. This generally includes new services or orders placed in EPIC for research subjects.*

If answered, "yes", this study will need to be set up in OnCore, Yale's clinical research management system, for Epic to appropriately route research related charges. Please contact [[contact]](mailto:[contact])

Are there any procedures involved in this protocol that will be performed at YNHH or one of its affiliated entities?

Yes  No

If Yes, please answer questions a through c and note instructions below.

a. Does your YNHH privilege delineation currently include the **specific procedure** that you will perform? Yes  No

b. Will you be using any new equipment or equipment that you have not used in the past for this procedure? Yes  No

c. Will a novel approach using existing equipment be applied? Yes  No

If you answered "no" to question 4a, or "yes" to question 4b or c, please contact the YNHH Department of Physician Services ([name]) for prior approval before commencing with your research protocol.

#### IMPORTANT REMINDER ABOUT RESEARCH AT YNHH

Please note that if this protocol includes Yale-New Haven Hospital patients, including patients at the HRU, the Principal Investigator and any co-investigators who are physicians or mid-level practitioners (includes PAs, APRNs, psychologists and speech pathologists) who may have direct patient contact with patients on YNHH premises must have medical staff appointment and appropriate clinical privileges at YNHH. If you are uncertain whether the study personnel meet the criteria, please telephone the Physician Services Department at [contact]. **By submitting this protocol as a PI, you attest that you and any co-investigator who may have patient contact has a medical staff appointment and appropriate clinical privileges at YNHH.**

### 1.2 BASELINE DESCRIPTIVE STATISTICS ANALYSIS

Baseline descriptive statistics will be reported for the overall study, site specific, and for both the control and treatment arms of the study. These will include patient age, gender race, ethnicity, and multiple comorbidities. We will compare baseline data by Chi Square (or Fischer's Exact) test for dichotomous/categorical variables and t-tests for continuous variables (unless the variables are non-parametric – in which case we will use a median test).

### 1.3 STUDY SUCCESS AND FAILURE CRITERIA

This study will be a success upon enrollment of 150 study participants and completion of 6 months follow-up.

### 1.4 SAMPLING PROCEDURE, SAMPLE SIZE AND POWER CALCULATION

The study sample size was calculated assuming 80% power to detect an effect size of 8.8 on the AFEQT questionnaire (slightly higher than the minimal clinically important difference of 5), with alpha 0.05.

We expect that drop-out rate will be close to zero in this study as patients are followed passively and the burden on patient is minimal. In terms of non-completion of the 6-month AFEQT Questionnaire, our

current study accounts for an estimated drop-out rate of 8% at 6 months based on the use of the AFEQT score from Holmes DN et al Circ Cardiovasc Qual Outcomes 2019, in which the mean  $\pm$  SD was  $79.0 \pm 18.5$  and assuming an effect size of 8.8 on the AFEQT questionnaire, which is higher than the minimal clinically important difference of 5.

If patient drop-out or loss to follow-up occurs, then we will carry forward the last patient-reported outcome measure response. If an electronic health record data connection is lost for a study participant, we will only include the follow-up duration when data were available in the utilization endpoint analyses.

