### **Analytic Plan**

Baseline characteristics to be collected will be patient age, sex, location of primary care, location of primary cardiac care, and the comorbidities mentioned above. At baseline, patients will also be queried about their likelihood to use personal digital devices for health care purposes outside of this study, including if they have previously used a personal digital device and if they have previously used a personal digital device for cardiovascular monitoring.

Primary Outcome: Difference in the Atrial Fibrillation Effect on QualiTy-of-life (AFEQT) questionnaire global score at 6 months compared to baseline

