## 1.5 ACCEPTANCE CRITERIA

We will accept all data received from study participants. If patients are missing primary outcome data, we will use the last observation carried forward for the PROMs.

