## 1.6 ENDPOINT ANALYSIS

### 1.6.1 PRIMARY ENDPOINT ANALYSIS

For the primary outcome, we will calculate the difference in the AFEQT global questionnaire score (as this is a continuous variable) at baseline and at 6 months and perform a comparison between the patients randomized to the Apple Watch and patients randomized to Withings Move. This will be calculated as per standard AFEQT calculations, which result in a summary score for this continuous outcome (which ranges from 0 to 100). We will use a t-test for this comparison. As this is an RCT, we expect that confounding will be minimal. If patients are missing outcome data, we will use the last observation carried forward for the patient-reported outcomes. Missing covariates will be set to missing.

At 12 months, we will also perform the same analysis, but this will be as an exploratory secondary endpoint. If a patient drops out, we will carry forward the most recent patient-reported outcome measure response.

We will also retrospectively compare AFEQT global questionnaire at months 1, 2, 3, 4, 5.

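### The sample size uses the SD of an AFEQT score, but the primary test is an unadjusted t-test on change, so the stated 80% power needs an unstated baseline to 6-month correlation of about 0.5 or more

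*SAP*

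**What the plan says.** **Sample size (SAP 1.4).** "The study sample size was calculated assuming 80% power to detect an effect size of 8.8 on the AFEQT questionnaire", at alpha 0.05. The SD is 18.5, quoted with a mean of 79.0 from a cited AFEQT study. Non-completion is allowed for: "current study accounts for an estimated drop-out rate of 8% at 6 months based on the use of the AFEQT score". The total is 150, randomised 1:1 (Protocol, Enrollment Procedure), and tests are two-sided at 0.05 (SAP 1.1).

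**Primary analysis (SAP 1.6.1).** The analysed quantity is a difference: "we will calculate the difference in the AFEQT global questionnaire score (as this is a continuous variable) at baseline and at 6 months". The method follows: "We will use a t-test for this comparison. As this is an RCT, we expect that confounding will be minimal". No baseline covariate is named. The Protocol's Analytic Plan defines the same outcome, the AFEQT "global score at 6 months compared to baseline".

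**Missing scores.** SAP 1.5 says "If patients are missing primary outcome data, we will use the last observation carried forward for the PROMs", and SAP 1.4 has the same rule for drop-out: "If patient drop-out or loss to follow-up occurs, then we will carry forward the last patient-reported outcome measure response". Up to 75 per arm may therefore enter the test.

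Neither document gives an SD of change or a baseline to 6-month correlation.

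**The concern.** On a 0 to 100 scale, a mean of 79.0 can only sensibly be a score level, so 18.5 reads as the spread between patients at one time. The spread of within-patient change is a different quantity. It is larger than 18.5 if the two scores are weakly correlated and smaller if they are strongly correlated. The power statement and the primary test therefore refer to different variables, and the figure that would link them is missing.

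The stated power of the only primary comparison is at stake. If the correlation is below about 0.5, the planned test has less than 80% power at 8.8 points, and a reader of the two documents cannot tell whether it is.

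**Working it through.** **Inputs.** Difference 8.8, SD 18.5, power 80%, 8% non-completion (SAP 1.4); two-sided 0.05 (SAP 1.1); 150 patients, 1:1. The correlation rho, and equal SDs at the two times, are assumptions.

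**1. Reproduce the plan's figure.** Normal approximation: n per arm = 2 × (1.960 + 0.842)² × 18.5² / 8.8² = 69.4, so 70 per arm and 140 in total; 140 / 0.92 = 152.2, so 153 against the planned 150. In reverse, 150 × 0.92 / 2 = 69 per arm. The standard error is 18.5 × √(2/69) = 3.15 and the noncentrality 8.8 / 3.15 = 2.79. With 136 df, power is 79.2%. The plan's figure is thus recovered with 18.5 entered directly as the SD of the tested variable. With 75 per arm it is 82.5%.

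**2. Largest SD that gives 80% power at 8.8** (noncentral t): 18.32 with 69 per arm, 19.11 with 75 per arm.

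**3. Convert to a correlation.** With SD 18.5 at both times, SD of change = 18.5 × √(2(1 − rho)). Solving for rho:
- 69 per arm: rho = 1 − (18.32/18.5)²/2 = 0.51
- 75 per arm, carried-forward scores keeping the full effect: rho = 1 − (19.11/18.5)²/2 = 0.47

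**4. Power at 8.8 points over a range of rho.** The ANCOVA residual SD is 18.5 × √(1 − rho²), with 135 df.

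| Assumed rho | SD of change | t-test on change, 69/arm | t-test on change, 75/arm | ANCOVA residual SD | ANCOVA, 69/arm |
|---|---|---|---|---|---|
| 0 | 26.2 | 50% | 53% | 18.5 | 79% |
| 0.3 | 21.9 | 65% | 69% | 17.6 | 83% |
| 0.4 | 20.3 | 72% | 75% | 17.0 | 86% |
| 0.5 | 18.5 | 79% | 82% | 16.0 | 89% |
| 0.7 | 14.3 | 95% | 96% | 13.2 | 97% |

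**5. Is ANCOVA ever worse?** For baseline SD s0 and 6-month SD s1, the change-score variance is s0² + s1² − 2·rho·s0·s1 and the ANCOVA residual variance is s1²(1 − rho²). Their difference is (s0 − rho·s1)², which is never negative. Apart from one degree of freedom, ANCOVA is never less precise, even with unequal SDs.

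**6. Limits of the gain.** ANCOVA still depends on the 6-month SD. If the SD were 22 at both times (an assumption), power with 69 per arm at rho 0.5 would be 77% by ANCOVA and 65% by the t-test on change, and ANCOVA would need rho of about 0.55 for 80%. Carrying scores forward also dilutes the effect. Suppose 8% of 75 per arm carry none of it and the residual SD is unchanged. The mean difference is then 8.8 × 0.92 = 8.10, and ANCOVA power is 76% at rho 0 and 79.7% at rho 0.3.

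**The case against.** **The sample size is arithmetically right, and 18.5 may be a fair SD of change.** This stands. Using 18.5 for change is the same as assuming rho = 0.5 with equal SDs, and nothing in the documents points to a lower value. If rho is above about 0.5, power exceeds 80%. A reader might infer that the trial is underpowered or that 150 is the wrong number; the documents support neither. A reader might also infer that the t-test is invalid. It is not: in a randomised comparison it is unbiased with correct Type I error, and only its precision is in question.

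**Carrying scores forward keeps 75 per arm and so relieves the problem.** Only in part. The threshold falls to 0.47 if carried scores keep the full effect. If 8% are carried with half the effect, it returns to about 0.51. One might go further and argue that carried-forward baselines push power well below the completers' figures. That overstates it: for those patients the change is exactly zero, so the SD shrinks along with the mean difference. In simulation with 6 of 75 per arm carried from baseline, power at rho 0.3 and 0.5 was about 63–65% and 78–79%, close to the figures for 69 completers. Monthly questionnaires also make it likely that a later score than baseline is the one carried.

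**ANCOVA is an efficiency gain and not the repair of an error.** True, and it is offered as that. It needs no rho near 0.5 only while the 6-month SD is near 18.5.

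**Baseline timing.** The Protocol's Enrollment Procedure gives priority to a pre-procedure baseline for cardioversion patients but enrols ablation patients on the day after the procedure. This differs by procedure and not by arm, so it does not suggest bias. It is a reason not to take a single rho with equal SDs for granted; no figure shows in which direction it moves rho.

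**Conclusion.** The point holds as a mismatch between the power calculation and the primary test. SAP 1.4 uses a score-level SD as if it were the SD of the analysed change. The 80% claim is then conditional on a correlation of about 0.51 or more (69 per arm), or about 0.47 or more (75 per arm with full effect in carried-forward scores), and neither document states one. Over assumed correlations of 0.3 to 0.7, the planned test's power with 69 per arm runs from 65% to 95%.

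This rests on reading 18.5 as a single-time-point SD, which follows from the SAP's own wording since the cited source was not consulted, and on SD 18.5 at both times. The missing correlation would by itself be a gap in reporting. The point deserves action because a more precise analysis is available from data already collected.

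**What to change.** Keep 150 patients.

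1. **SAP 1.6.1:** replace the unadjusted t-test with an ANCOVA of the 6-month AFEQT global score on arm and baseline AFEQT. Using the change as the outcome gives the same arm difference and standard error, because the two outcomes differ only by a covariate already in the model. The Protocol's definition of the primary outcome can therefore stay as it is.
2. **SAP 1.4, companion edit:** state the SD and the correlation assumed for the analysed quantity, and show power over a plausible range of both.
3. **Missing baseline:** give a rule for patients without a baseline AFEQT, since SAP 1.6.1 says only "Missing covariates will be set to missing". The change score already needs the same value, so this is no new data requirement.

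**Cost:** one dated SAP amendment and no added patients, visits or data. Timing matters. Enrollment was to begin in August 2021, data are cleaned and reviewed on a rolling basis (Protocol, Probable Duration of Project), and the SAP is dated August 11, 2022. The amendment should be made, and be seen to be made, before any outcome is compared by arm.

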## 1.5 ACCEPTANCE CRITERIA

We will accept all data received from study participants. If patients are missing primary outcome data, we will use the last observation carried forward for the PROMs.

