As an exploratory outcome, we will aim to assess differences between SpO2 from the Apple Watch and medical grade readings.

The metrics we plan to collect are as follows:

A. Enrollment-related

- Number of people asked for study participation and number enrolled
  - Among patients who decline enrollment, if willing, the reason for declining

B. PROM-related (for all PROMs)

- Proportion of items completed
- Content of PROM responses

C. Personal Digital Device-related

- Number of patients who obtain Apple Watch ECGs over the study period, and the number of ECGs obtained
- Number of patients who receive an irregular rhythm notification during the study period, and the number of irregular rhythm notifications per patient
- Data obtained from Apple HealthKit and Withings Move

As each patient completes 12 months of follow-up, all patient data will be sent to the Mayo Clinic, where an analyst will clean and curate the data made available through the Hugo platform.

Finally, at the official end of the study (i.e. at 12 months post-procedure), study participants will receive a close-out questionnaire (see below) to assess occurrence of atrial fibrillation/atrial flutter, quality of life, anticoagulation medications, and device usage.

**4. Genetic Testing**      N/A

**5. Subject Population:** Provide a detailed description of the types of human subjects who will be recruited into this study.

We will recruit a total of 60 study participants undergoing cardioversion for atrial fibrillation or atrial flutter at Yale-New Haven Hospital. Yale-New Haven Hospital in New Haven, CT sees over 79,000 patients a year with

approximately 65,000 adult patients and there are approximately 1 to 3 cardioversions performed daily as well as more than 700 ablations annually.

6. **Subject classification:** Check off all classifications of subjects that will be specifically recruited for enrollment in the research project. Will subjects who may require additional safeguards or other considerations be enrolled in the study? If so, identify the population of subjects requiring special safeguards and provide a justification for their involvement.

Pregnant women or females of childbearing potential have the potential of being enrolled in this study but will not be specifically recruited for enrollment preferentially over other patients. We anticipate that this study presents minimal risk to pregnant women.

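### Last observation carried forward is the only rule for missing AFEQT scores; nothing in the plan tests it or reports completion by arm

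*SAP*

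**What the plan says.** Three sections of the SAP give the same rule.

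- SAP 1.4: "If patient drop-out or loss to follow-up occurs, then we will carry forward the last patient-reported outcome measure response".
- SAP 1.5: "If patients are missing primary outcome data, we will use the last observation carried forward for the PROMs".
- SAP 1.6.1: "If patients are missing outcome data, we will use the last observation carried forward for the patient-reported outcomes".

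On the analysis of change from baseline to month 6, SAP 1.6.1 says: "We will use a t-test for this comparison". On the amount of missing data, SAP 1.4 says "We expect that drop-out rate will be close to zero in this study" and then that the "current study accounts for an estimated drop-out rate of 8% at 6 months", the latter referring to the 6-month AFEQT.

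Two items come close to a check but are not one. The Protocol's list of metrics includes "Proportion of items completed" for the questionnaires, without saying by arm or by month. SAP 1.6.1 adds: "We will also retrospectively compare AFEQT global questionnaire at months 1, 2, 3, 4, 5". That compares the arms at earlier visits; it does not ask what the missing month-6 scores would have been.

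**The concern.** Carrying the last score forward assumes that a patient's AFEQT stops moving after the last response. The trial measures AFEQT around a procedure intended to change symptoms, and the endpoint is change over six months. For cardioversion patients the Protocol (Enrollment Procedure) prioritises completing the baseline survey before the procedure. Applied literally, the rule gives such a patient who never answers again a change of exactly zero. The SAP does not address the baseline-only case.

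Two kinds of error follow. If the arm effect is still growing, frozen scores dilute it. If missingness, or its timing, differs by arm while scores are moving, the frozen scores bias the comparison in either direction, even when there is no true effect.

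Unequal response is plausible but not established. Controls are paid as they answer surveys, while Watch patients keep the device with an expectation that they will respond (Protocol, Follow-Up and Payments for Participation). The documents do not show which arm would respond less. Both arms receive two reminders and a telephone call through month 6, which limits the problem without removing it.

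**Working it through.** **Inputs from the documents.** 150 patients randomised 1:1, so 75 per arm; difference 8.8; SD 18.5 and mean 79.0 from the study cited in SAP 1.4; two-sided alpha 0.05; 8% non-completion; AFEQT monthly to month 6.

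**The plan's own figure.** 75 × 0.92 = 69 per arm. 8.8 / (18.5 × √(2/69)) = 2.79, which gives 79.8% power. The stated 80% reproduces. Carrying scores forward does not analyse 69 per arm. It keeps up to 75, of whom 75 × 0.08 = 6 per arm have a frozen score.

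**Assumptions, because the documents are silent.** Correlation between visits 0.5 (so the SD of change is also 18.5); arm effect building linearly to 8.8; a gain G at month 6 common to both arms, following 0, 6, 9, 11, 13, 14, 15 over months 0 to 6, rescaled to G.

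**How large G can be.** On a 0–100 scale the variance cannot exceed m(100 − m). With 18.5² = 342.25, the highest possible mean is 50 + √(2500 − 342.25) = 96.45. From a baseline mean of 79.0, G is at most 96.45 − 79.0 − 8.8 = 8.65. G = 15 needs a baseline mean of 96.45 − 15 − 8.8 = 72.65 or lower.

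**Expected estimate.** Let pW and pC be the shares missing in the Watch and control arms, and let f and s be the shares of the effect and of the common gain already reached at the carried month:

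estimate = 8.8 × [1 − pW(1 − f)] − (pW − pC)(1 − s)G

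Month 5 carried: f = 5/6, s = 14/15. Month 3: f = 1/2, s = 11/15. Baseline: f = s = 0.

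Worked example, 12% Watch / 4% control, baseline carried, G = 8.65: 8.8 × 0.88 − 0.08 × 8.65 = 7.74 − 0.69 = 7.05.

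Power is from 40,000 simulated trials per scenario, using the unadjusted t-test, with missingness random per patient (simulation error at most 0.25 percentage points).

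| Missing (Watch/control) | Carried from | G | Expected difference | Power |
|---|---|---|---|---|
| 8%/8% | month 5 | any | 8.68 | 81.4% |
| 8%/8% | month 3 | any | 8.45 | 79.1% |
| 8%/8% | baseline | 5 to 15 | 8.10 | 78.3% to 75.7% |
| 12%/4% | month 5 | 8.65 | 8.58 | 80.6% |
| 12%/4% | month 3 | 8.65 | 8.09 | 75.8% |
| 12%/4% | baseline | 8.65 | 7.05 | 65.5% |
| 12%/4% | baseline | 15 | 6.54 | 57.2% |

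**Reversed split, 4%/12%.** At G = 8.65 the same formula gives 8.79 with month 5 carried and 8.81 with month 3, so almost no error. With baseline carried it gives 8.8 × 0.96 + 0.69 = 9.14, or 9.65 at G = 15: overestimates.

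**No true effect, 12%/4%.** The bias is −(pW − pC)(1 − s)G. At G = 8.65 this is −0.05, −0.2 and −0.7 for month 5, month 3 and baseline; at G = 15 with baseline carried it is −1.2. With baseline carried, type I error is 5.8% (G = 8.65) and 7.0% (G = 15). With exactly 9 and 3 patients missing it is 5.3% and 6.1%.

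**What a mixed model changes.** At G = 8.65, 5,000 trials per scenario (error about 0.4 percentage points), its mean estimate is 8.7 to 8.8 with type I error of 4% to 5%. Baseline adjustment has to be separated out, because it raises power whichever way missing scores are handled:

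| Missing | Method | Month 5 | Month 3 | Baseline |
|---|---|---|---|---|
| 8%/8% | carried forward + baseline adjustment | 90.8% | 89.1% | 86.6% |
| 8%/8% | mixed model | 89.3% | 89.3% | 90.0% |
| 12%/4% | carried forward + baseline adjustment | 90.3% | 86.5% | 75.8% |
| 12%/4% | mixed model | 90.2% | 89.5% | 88.9% |

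Replacing the carry-forward rule itself therefore changes power by about −1 to +3 points at 8%/8% and 0 to +13 at 12%/4%. Nor is the mixed model immune. If non-responders in both arms truly score 10 points below its prediction, it is off by (0.12 − 0.04) × 10 = 0.8 points.

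**The case against.** The strongest reply is that nothing material goes wrong on the SAP's own figures. At 8% in each arm, with month 5 or month 3 carried, power is 81% or 79% against a planned 79.8%. Two reminders and a call support each survey, so early and complete silence should be rare. This stands: the damage at the planned rate is modest.

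The unequal-missingness figures also use G at its mathematical ceiling. A mean of 96.45 with SD 18.5 would require every patient to score 0 or 100. At 12%/4% with baseline carried, smaller gains give about 72% power (G = 3) or 70% (G = 5), null bias of −0.24 or −0.40, and type I error near 5%. This too stands; the lowest power figures are bounds, not forecasts.

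The trajectory and the direction of the split are assumptions. An effect that peaks early and fades would be overstated, not diluted. That is correct, but an error of unknown sign is a reason to test the rule, not to rely on it alone.

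The month 1–5 comparisons would show whether the arm difference is still growing. They would help in reading the result, but they neither show who is missing nor vary the assumption about them.

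Finally, a sensitivity analysis and a completion table might be enough, and changing the primary analysis after enrolment has begun needs care: enrolment was due to start in August 2021 and the SAP is dated August 2022. The timing point is fair and is met by fixing the change before the arms are compared. Much of the mixed model's power advantage is indeed baseline adjustment, as the working shows.

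**Conclusion.** The point holds and should be fixed. The sole primary result rests on one untested assumption about non-responders, and no planned analysis would show whether it mattered.

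The likely size is small. At 8% missing in both arms, between 0.1 and 0.7 of the 8.8 points are lost. If non-completers miss only month 6, which fits the SAP's expectation of near-zero drop-out, the loss is at the bottom of that range. It becomes material only if non-completers stop early and unequally by arm: up to 1.75 points lost (8.8 − 7.05) at G = 8.65 and 2.26 (8.8 − 6.54) at G = 15, or an overestimate of 0.3 to 0.85 if the split is reversed. Those baseline-carried cases require every non-completer to miss all six monthly surveys.

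The text of the plan is clear. Confidence in the size is only moderate, because the trajectory, the trial's baseline mean, the correlation and the by-arm missingness are all assumed.

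**What to change.** In SAP 1.4, 1.5 and 1.6.1, before the arms are compared:

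1. Make the primary analysis a mixed model for repeated measures on the monthly AFEQT scores, with arm, month, arm × month, baseline AFEQT × month and an unstructured covariance. The month-6 arm contrast is the estimate.
2. Keep the carried-forward analysis as a sensitivity analysis, and state how baseline-only patients are handled in it.
3. Add a delta-adjusted multiple-imputation analysis that retains every randomised patient, including those with only a baseline score.
4. Report AFEQT completion by arm and month.

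The cost is SAP wording and some extra programming; no new data are needed. The mixed model relies on data being missing at random and gets no month-6 information from baseline-only patients; item 3 probes both. If only month 6 is missed, the model gains nothing over a carried-forward analysis adjusted for baseline. If the investigators keep the current primary analysis, items 3 and 4 are still needed.
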